5.7 Premature Termination of the Trial

The clinical trial may be terminated prematurely or suspended at the request of Health Authorities or if new safety or efficacy information leads to an unfavorable risk benefit judgment for any IMP. The Sponsor may discontinue the trial if the trial becomes unjustifiable for medical or ethical reasons, the trial experiences poor enrollment, or due to discontinuation of clinical development of an IMP or withdrawal of an IMP or comparator from the market for safety reasons.

Health Authorities and IECs/IRBs will be informed about the discontinuation of the trial in accordance with applicable regulations.

5.8 Definition of End of Trial

A participant is considered a study completer if one of the following conditions applies:

• The participant has completed the 4-week Safety Follow-up Visit/End of Trial Visit (main or OLE study), even if the participant discontinued treatment prematurely.

OR

• The participant has completed the OLE End of Treatment Visit and is entering the long-term follow-up study under a new protocol.

Participants who are not continuing the treatment in the long-term follow-up study under a new protocol, must attend an OLE End of Treatment Visit followed by a 4-week Safety Follow-up Visit/End of Trial Visit of the OLE Period to complete the study under the current protocol. Participants who are entering the long-term follow-up study under a new protocol, are neither required to enter the 4-week Safety Follow-up Period nor to undergo a 4-week Safety Follow-up Visit/End of Trial Visit to complete the study under the current protocol. These participants must attend the OLE End of Treatment Visit to be considered study completers.

The end of the study is defined as the last contact date with the last participant who participates in this trial (last participant's last visit). A clinical trial protocol may not be considered closed as long as:

- Any participant is still receiving any IMP;
- Visits specified by the protocol are still taking place;
- Procedures or interventions according to the protocol are still being undertaken in any participant;
- The post-treatment follow-up period, defined in the clinical trial protocol as being part of the trial, has not yet been completed for any participant.

Investigational Medicinal Product and Other Drugs Used in the Trial

The term "Investigational Medicinal Product" refers to the investigational drug undergoing study (i.e., M2951), the placebo and the reference therapy, Tecfidera.

6.1 Description of the Investigational Medicinal Product

Investigational Medicinal Product M2951 and placebo: dose/mode of administration/ dosing schedule:

The drug substance M2951, chemical name 1-(4-{[6-Amino-5-(4-phenoxy-phenyl)-pyrimidin-4-ylamino]-methyl}-piperidin-1-yl)-propenone, is a white to yellow powder.

M2951 will be administered as white tablets ready for oral administration containing 25 mg of drug substance formulated with excipients. The placebo will be administered as white tablets ready for oral administration matching the active both in color and in size.

The Sponsor will provide M2951 and placebo to the trial site, manufactured and tested according to applicable current GMP requirements for clinical trial supplies and a confirmation of release for human use in clinical trials.

Reference therapy Tecfidera: dose/mode of administration/dosing schedule (17, 18):

The active control group will receive Tecfidera. For the first 7 days, Tecfidera is given 120 mg twice daily orally. Following this, and for the duration of treatment, it is given 240 mg twice daily orally. For sites in the EU, Tecfidera will be centrally sourced and provided by the Sponsor. For sites in the USA, Tecfidera will be locally sourced at each trial site according to local regulations. Tecfidera should be administered according to the local label and applicable regulations.

6.2 Dosage and Administration

Participants will receive 25 mg once daily, 75 mg once daily, or 75 mg twice daily M2951 or placebo administered as tablets for 168 days. To maintain blinding for placebo and M2951 (see Section 6.9), participants will self-administer study medication at a schedule similar to the 75 mg M2951 twice daily dosing schedule (i.e., 3 tablets twice daily). At the end of the 24-week treatment period, it is intended to switch the placebo group to M2951 at a dose of 25 mg once daily; however, flexibility will be maintained to allow adjusting this dose based on data from the primary analysis.

Participants who entered the OLE Period initially received M2951 at 75 mg once daily. After review of the efficacy and safety data from the primary analysis at 24 weeks and the blinded extension analysis at 48 weeks, the optimal tested dose is 75 mg twice daily. Accordingly, once IMP for this dose is available at the study site, participants participating in the OLE Period will either enter the OLE Period on the 75 mg twice daily dose or will be switched to the 75 mg twice daily dose. Participants who do not participate in the OLE Period will no longer receive M2951 or Tecfidera.

If a dose is missed, the participant can take the missed dose up to 6 hours after the scheduled time. If more than 6 hours have elapsed since the dose was missed, the participant should skip the dose for that period, make note of the missed dose, and take the next dose at the regularly scheduled time.

When visits are scheduled to occur (see Section 7.5) the participant should refrain from taking their scheduled morning dose and take their dose of IMP when instructed at the visit.

Participants will be asked to record the date and time of dosing and food intake around dosing in a participant diary. Participants will self-administer the IMP at a set time each day (every 12 hours \pm 2 hours). Participants must take their daily dose more than 1 hour prior to a meal or snack and more than 2 hours after a meal or snack. Clear fluids are allowed at any time. On trial visit days, the IMP will be administered during the trial visit after the scheduled trial visit procedures (other than post-treatment \bigcirc) are completed.

Participants who develop GI or flushing disturbances while receiving Tecfidera may reduce their study treatment dose by taking 120 mg twice daily for 1 month at the Investigator's discretion. After 1 month at the reduced dose, participants will resume the 240 mg twice daily dosing. If the participant is still unable to tolerate the study treatment, the participant must permanently discontinue study treatment as described in Section 6.4.4.2.

6.3 Assignment to Treatment Groups

Eligible participants will be randomized 1:1:1:1:1 to treatment with placebo, low-dose M2951 (25 mg once daily), mid-dose M2951 (75 mg once daily), high-dose M2951 (75 mg twice daily), or Tecfidera (administered twice daily at a final dose of 240 mg), through a central randomization process by an IWRS prior to dosing on Day 1. Stratification will occur by region (USA or Western Europe, Eastern Europe and CCl., Eastern Europe and not CCl., and RoW). For the first 7 days, Tecfidera is administered orally at 120 mg twice daily. Following this and for the duration of treatment, Tecfidera is administered orally at 240 mg twice daily. Participants who entered the OLE Period initially received M2951 at 75 mg once daily. After review of the efficacy and safety data from the primary analysis at 24 weeks and the blinded extension analysis at 48 weeks, the optimal tested dose is 75 mg twice daily. Accordingly, once IMP for this dose is available at the study site, participants participating in the OLE Period will either enter the OLE Period on the 75 mg twice daily dose or will be switched to the 75 mg twice daily dose.

6.4 Concomitant Medications and Therapies

All concomitant medications taken by the participant during the trial, from the date of signature of informed consent are to be recorded in the appropriate section of the eCRF, noting the name, dose, duration, regimen, and indication of each drug. Nondrug interventions and any changes to a concomitant medication or other intervention should also be recorded in the eCRF. Concomitant medications and procedures will be recorded at Screening and Day 1, and any changes elicited/recorded at every trial visit.

6.4.1 Permitted Medicines

Permitted medications are any medications required per the medical history and not specifically prohibited by the protocol during the trial. These standard of care medications are part of the participant's previous treatment and will therefore not be provided by the Sponsor. Any such medications prescribed or used should be recorded in the eCRF.

Participants who experience an MS relapse (see Section 7.3.3) during treatment may receive rescue medication participant to the following restrictions:

• Up to 1 g daily of methylprednisolone administered IV for up to 5 consecutive days.

Oral tapering of corticosteroid rescue medication is permitted, with a maximum of 15 days of tapering allowed.

Participants should not be withdrawn from treatment with trial medication solely because of the occurrence of a relapse unless they meet the criteria for withdrawal (see Section 5.6).

Note: Where possible, the use of high dose corticosteroids should be avoided in the 3 weeks prior to a scheduled MRI scan.

Any medications (other than those excluded as per exclusion criteria in Section 5.3.2 or prohibited as per Section 6.4.2) that are considered necessary for the participants' welfare and will not interfere with the trial medication may be given at the Investigator's discretion.

6.4.2 Prohibited Medicines

Medications prohibited before the trial are listed in the exclusion criteria (Section 5.3.2).

[figure not shown]
The following medications and therapies are not permitted during the trial and would require discontinuation of the trial treatment:

- Initiation of an immunosuppressant or immunomodulator, such as cladribine, cyclophosphamide, azathioprine.
- New therapies for MS should not be initiated during the trial. Initiation of any new immunosuppressant or immunomodulatory therapy would be considered a treatment failure and should result in withdrawal of the participant from the IMP (see Section 5.6.1).

- Oral or parenteral steroids, except rescue medication to treat a relapse of MS, or adrenocorticotropic hormone. For participants experiencing a treatment gap (as described in Section 7.1.6), these medications can be administered only during that gap period if medically indicated, and must be discontinued prior to restarting study treatment.
- Biologic therapies.
- IV Ig therapy and/or plasmapheresis.
- Treatment with teriflunomide.
- Daclizumab.
- Live and live-attenuated vaccines.
- Medications known to lower the seizure threshold should be avoided. If treatment with these medications is required, the Investigator must inform the Medical Monitor.
- Initiation or dose changes of dalfampridine (Ampyra) or fampridine during OLE Period is permitted only in case the participant has been on a stable dose of evobrutinib for at least 3 months prior to initiation or dose change.
- Changes in dalfampridine dose (participant must be on a stable dose).
- Herbal supplements including, but not limited to, St. John's wort, grapefruit, Seville oranges, cranberries, or juices of these fruits.
- Any investigational drug within 1 month or 5 half-lives of the investigational drug, whichever is longest, prior to Screening.
- Moderate or strong inhibitors or inducers of CYP3A or drugs mainly metabolized by CYP3A with a narrow therapeutic index. The list in Table 6 is not meant to be a complete list of all CYP3A inhibitors, inducers, or substrates with a narrow therapeutic range. Study sites should consider each medication on a case-by-case basis and discuss with the Medical Monitor. The additive effects of weak inhibitors taken in combination must also be taken into account. For participants experiencing a treatment gap (as described in Section 7.1.6), these medications can be administered only during that gap period if medically indicated, and must be discontinued prior to restarting study treatment.
- Any investigational drug or experimental procedure for MS.

6.4.2.1 Use of Prohibited Medications in the Treatment Gap

A gap in study drug treatment during the OLE Period after Week 96 may occur as described in Section 7.1.6.

If the Investigator considers alternate RMS treatment appropriate during the treatment gap, and the participant opts to resume study drug after the treatment gap the following guidelines should be applied:

- Study drug can be resumed after β-interferon or glatiramer acetate treatment discontinuation with no washout period;
- Study drug can be resumed 4 weeks after tecfidera treatment discontinuation;
- Study drug can be resumed 12 days after teriflunomide treatment discontinuation only if an accelerated elimination procedure is followed prior to resumption of study drug;
- If an RMS treatment other than those above is preferred, the participant will not be able to restart the study drug and should instead enter the 4-week Safety Follow-up Period.

Any alternate RMS treatment administered during a treatment gap should be used according to the local label and local guidelines.

Participants still on the study should at no point be receiving study drug and an alternate RMS treatment at the same time.

Other Interventions 6.4.3

Not applicable.

6.4.4 **Special Precautions**

6.4.4.1 For M2951 Only

The IMP should be temporarily withheld or permanently withdrawn if the following abnormalities occur or reoccur (also see Table 7), as relevant, and reinitiation following temporarily withholding of IMP should be discussed with the Medical Monitor. If a participant's OLE predose or OLE baseline value is abnormal and/or falls within any of the below criteria, consult with the Medical Monitor regarding potential withdrawal, continued participation in study, and additional monitoring if needed. Retesting should be completed within 1 week:

- For a neutrophil count < 500/mm³ or platelet count < 25,000/mm³ (Grade 4) or neutrophil count 500 to 999/mm³ with fever (Grade 3) or platelet count 25,000 to 49,999/mm³ (Grade 3) with bleeding, the IMP should be permanently withdrawn.
- For a Grade 3 decrease in neutrophil count without fever or Grade 3 decrease in platelet count without bleeding, temporarily hold the IMP and recheck the value. If the value is still Grade 3, permanently discontinue the IMP.
- For a Grade 2 decrease in neutrophil count (1,000 to 1,499/mm³) or Grade 2 decrease in platelets counts (50,000 to 74,999/mm³), temporarily hold the IMP and recheck the value. Reinitiate the IMP after discussion with the Medical Monitor if no further downward trend is observed.

The Investigator is required to discontinue the study treatment for abnormal liver function when a participant meets one of the conditions outlined below or if the Investigator believes that it is in best interest of the participant. Liver function test-related monitoring and discontinuation criteria should be based on both central and local laboratory assessments depending on availability (i.e., participants should be discontinued if central or local laboratory result fulfills related criterion). The final decision should be based on the highest reported values (regardless of central or the local laboratory evaluation).

- For an increase in AST and/or ALT to > 3× ULN in combination with an increase in total bilirubin to > 2 × ULN, the study treatment should be permanently discontinued and the Medical Monitor informed. In addition, a comprehensive hepatic/autoimmune panel is required.
- For an increase of ALT/AST \geq 5 ULN (without increased bilirubin values) or increase of total bilirubin > 2 ULN (without increased ALT/AST values) the study treatment should be permanently discontinued and the Medical Monitor informed. In addition, a comprehensive hepatic/autoimmune panel is required.

Decision about discontinuation of the study treatment due to elevated LFTs after 24 weeks of exposure to evobrutinib may be taken on a case-by-case basis in consultation with the Medical Monitor.

For any study treatment discontinuation related to laboratory or assessment results, the participant should be followed with additional testing as needed until a return to within normal limits or an acceptable value. In cases for which permanent discontinuation of study treatment is required, no rechallenge will be allowed.

Liver Function Testing criteria:

- For an increase in AST or ALT to $> 3 \times$ to $< 5 \times$ ULN, temporarily interrupt the study intervention and recheck the value within 72 hours to confirm the reported elevation.
- If AST and/or ALT $> 3 \times ULN$ to $< 5 \times ULN$ are confirmed within 72 hours and have increased by more than 50% (compared to latest confirmed value), continue interruption of the study intervention with an additional recheck in 72 hours later.
 - o If rechecked value in the second recheck has decreased to < ULN or < participant's baseline, rechallenge can be considered in the absence of hyperbilirubinemia.
 - In all other cases, permanently discontinue the study intervention and inform the Medical Monitor.
- If AST and/or ALT $> 3 \times$ ULN to $< 5 \times$ ULN are confirmed within 72 hours and have increased by less than 50% (compared to latest confirmed value), continue interruption of the study intervention with an additional recheck in 1 week.
 - o If rechecked value in the second recheck has decreased to < ULN or < participant's baseline, rechallenge can be considered in the absence of hyperbilirubinemia.
 - In all other cases, permanently discontinue the study intervention and inform the Medical Monitor.
- For an increase in bilirubin of $> 1.5 \times \text{to} \le 2 \times \text{ULN}$, temporarily interrupt the study intervention and recheck the value within 72 hours to confirm the reported elevation.
 - o If the value is still $> 1.5 \times$ to $\le 2 \times$ ULN upon recheck, continue temporary interruption of the study intervention with an additional recheck in 1 week.
 - If the value is still $> 1.5 \times \text{to} \le 2 \times \text{ULN}$ upon second recheck, the study intervention should be permanently discontinued and the Medical Monitor informed.
 - o If the value has decreased to $\leq 1.5 \times ULN$, the Investigator may reinitiate study intervention.

Any rechallenge associated with LFT elevations should follow a weekly monitoring for 12 weeks.

For participants who temporarily or permanently discontinue study treatment because of abnormal liver function consultations with specialists, such as a hepatologist and liver imaging such as ultrasound are encouraged to exclude potential alternative causes of liver injury.

A comprehensive hepatic panel is requested for participants for whom withdrawal criteria (see Section 5.6.1) are met or who permanently or temporarily discontinue dosing because of elevated transaminases. Testing should include screening for the following:

- o International normalized ratio (INR), partial thromboplastin time, fibrinogen, high sensitivity C reactive protein
- Anti-Hepatitis A Virus (anti-HAV) IgG and IgM, HBsAg, anti-Hepatitis B Core Antigen (anti-HBc) IgM, anti-HBsAg, anti-HCV (6 weeks or later post-initial LFTs elevation), anti-Hepatitis E Virus (anti-HEV) IgG and IgM, antiviral capsid antigen (anti-VCA) IgG and IgM, anti-early antigen (anti-EA) IgG, antiEpstein-Barr

- Nuclear Antigen (anti-EBNA) IgG, anti-cytomegalovirus (CMV) IgG and IgM, Epstein-Barr virus (EBV) polymerase chain reaction (PCR), and CMV PCR
- o HCV RNA by PCR
- o Antinuclear antibody, antismooth muscle antibody, antibody to liver-kidney microsomes
- o Alkaline phosphatase, albumin, ALT, AST, GGT, and total bilirubin
- o Ferritin and transferrin saturation

CCI

- For an increase in amylase or lipase to $> 5 \times$ ULN (Grade 4), the IMP should be permanently withdrawn.
 - For an increase in amylase or lipase to > 2 to 5× ULN (Grade 3), temporarily hold the IMP and recheck the value within 24 hours of receipt. If the value is still Grade 3, permanently discontinue the IMP.
 - For an increase in amylase or lipase to Grade 2 (> 1.5 2× ULN), temporarily hold the IMP and recheck the value within 24 hours of receipt. Discontinue the IMP if the value does not decrease or reinitiate the IMP after discussion with the Medical Monitor if a downward trend is observed.
- For an increase in serum creatinine to $> 3 \times$ from Baseline (Grade 3 or higher), the IMP should be permanently withdrawn.
 - For any other increase in serum creatinine > 1.5 3.0× from Baseline (Grade 2), temporarily hold the IMP and recheck the value within 24 hours of receipt. Discontinue the IMP if the value does not decrease, or reinitiate the IMP after discussion with the Medical Monitor if a downward trend is observed.
- For any other laboratory abnormality of Grade 4 severity, the IMP should be permanently withdrawn.
 - For any other laboratory increase/decrease (as relevant) from Baseline to a clinically significant higher severity grade, temporarily hold the IMP and recheck the value within 24 hours of receipt. Discuss restarting the IMP with the Medical Monitor if an improving trend is observed.
 - For an absolute lymphocyte count < 200/mm³ (Grade 4), should be temporarily withdrawn and follow-up testing should be conducted. When the absolute lymphocyte count returns to ≥ 800/mm³ (i.e., returns to Grade 1), IMP can be resumed.

Table 7 Guidelines for Withholding or Permanent Withdrawal of IMP

Parameters	Grade 1	Grade 2	Grade 3	Grade 4		
Neutrophil count	-	1,000 - 1,499/mm ^{3 b}	500 - 999/mm ^{3 a}	< 500/mm ³		
decrease		< 1.5 - 1.0× 10 ⁹ /L ^b	< 1.0 - 0.5× 10 ⁹ /L ^a	< 0.5× 10 ⁹ /L		
Neutrophil count	-	-	500 - 999/mm ³	< 500/mm ³		
decrease with fever			< 1.0 - 0.5× 10 ⁹ /L	< 0.5× 10 ⁹ /L		
Platelet count	-	50,000 - 74,999/mm ³	25,000 - 49,999/mm ³	< 25,000/mm ³		
decrease		D	a	< 25.0× 10 ⁹ /L		
		< 75.0 - 50.0× 10 ⁹ /L ^b	< 50.0 - 25.0× 10 ⁹ /L ^a			
Platelet count	-	-	25,000 - 49,999/mm ³	< 25,000/mm ³		
decrease with bleeding			< 50.0 - 25.0× 10 ⁹ /L	< 25.0× 10 ⁹ /L		
Amylase or lipase increase	-	> 1.5 - 2.0× ULN °	> 2.0 - 5.0× ULN ^a	> 5.0× ULN		
Serum creatinine increase	-	> 1.5 - 3.0× baseline °	> 3.0× baseline	> 6.0× ULN		
Absolute	< LLN - 800/mm ³	500 - 799/mm ³	200 - 499/mm ³	< 200/mm ^{3 d}		
lymphocyte count decrease	< LLN - 0.8× 10 ⁹ /L	< 0.8 - 0.5× 10 ⁹ /L	< 0.5 - 0.2× 10 ⁹ /L	< 0.2× 10 ⁹ /L ^d		
ALT, AST and Bilirubin Increase						
AST or ALT increase	>3.0 - < 5.0× ULN ^e		≥ 5.0× ULN			
AST or ALT with bilirubin increased > 2× ULN	> 3.0x ULN					
Bilirubin increase	>1.5 - ≤2× ULN ^e		> 2× ULN			

ALT=alkaline aminotransferase, AST=aspartate aminotransferase, IMP=investigational medicinal product, LLN=lower limit of normal, ULN=upper limit of normal.

IMP should be permanently withdrawn.

- a. Temporarily withhold and recheck value. If the value is still Grade 3, permanently discontinue the IMP.
- Temporarily withhold IMP and recheck the value. Reinitiate the IMP after discussion with the Medical Monitor if no further downward trend is observed.
- c. Temporarily withhold IMP and recheck the value. Reinitiate the IMP after discussion with the Medical Monitor if a downward trend is observed.
- d. Temporarily withhold IMP and follow-up testing should be conducted. When the absolute lymphocyte count returns to Grade 1, IMP can be resumed.
- e. Temporarily withhold IMP and recheck value per Liver Function Testing criteria above. For participants who temporarily or permanently discontinue study treatment because of abnormal liver function consultations with specialists, such as a hepatologist and liver imaging such as ultrasound are encouraged to exclude potential alternative causes of liver injury and the Medical Monitor should be informed.

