5.6.1 Withdrawal from Trial Therapy

Participants who withdraw from therapy (during the 48-week main study or OLE Period) must immediately return for an End of Treatment Visit or an OLE End of Treatment Visit followed by the 4-week Safety Follow-Up/End of Trial Visit 4 weeks later (see Section 7.1.5 and 7.1.6). A participant must be withdrawn if any of the following occur:

- Withdrawn from study (see Section 5.6.2);
- AEs, if discontinuation of IMP is desired or considered necessary by the Investigator and/or participant;
- Use of prohibited medications, as defined in Section 6.4.2. However, any medications that are considered necessary for the participant's well-being may be given at the discretion of the Investigator. Use of a prohibited medication may be cause for a participant to withdraw, however each incident should be discussed on a case-by-case basis with the study and Medical Monitor;
- Pregnancy;
- Lack of efficacy and/or progression of MS as defined by Investigator judgment or when a medication other than protocol-allowed medications is needed for treatment;
- Any events that unacceptably endanger the safety of the participant;
- IMP will be discontinued in case of elevated liver tests as defined in protocol Section 6.4.4.
- If any of the following occur while a participant is receiving Tecfidera (17, 18):
 - Any instance of lymphocyte counts < 200/mm³ or < 500/mm³ for > 24 weeks
 - In the event of serious infection, Tecfidera should be withheld until the infection is resolved
 - At the first sign or symptom suggestive of PML
 - More than 1 instance of dose reduction due to a flushing reaction (see Section 6.4.4 or the local label [17, 18]) and GI disturbances.

Withdrawal due to special precautions is described in Section 6.4.4.

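### After 24 weeks of evobrutinib, Section 6.4.4.1 allows the combined ALT/AST and bilirubin stop to be decided case by case, so it is no longer unconditionally mandatory

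*Protocol*

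**What the plan says.** Section 6.4.4.1 of the protocol opens with a general rule for evobrutinib: "The IMP should be temporarily withheld or permanently withdrawn if the following abnormalities occur or reoccur (also see Table 7"). Restarting after a hold is to be discussed with the Medical Monitor.

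The liver paragraph is firmer: "The Investigator is required to discontinue the study treatment for abnormal liver function when a participant meets one of the conditions outlined below". Three immediate criteria follow. The first is AST and/or ALT > 3× ULN together with total bilirubin > 2× ULN, for which "the study treatment should be permanently discontinued and the Medical Monitor informed". The others are ALT/AST ≥ 5× ULN without raised bilirubin, and total bilirubin > 2× ULN without raised ALT/AST. They carry the same instruction.

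The next sentence says that the decision to discontinue because of "elevated LFTs after 24 weeks of exposure to evobrutinib may be taken on a case-by-case basis in consultation with the Medical Monitor". The paragraph after it bars rechallenge, but only in cases where permanent discontinuation is required.

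Table 7 lists the same three thresholds. Its key includes the line "IMP should be permanently withdrawn". Its one liver footnote, e, marks the lower ranges and reads "Temporarily withhold IMP and recheck value per Liver Function Testing criteria above". Section 5.6.1 says "IMP will be discontinued in case of elevated liver tests as defined in protocol Section 6.4.4".

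**The concern.** Drug-induced liver injury is the important identified risk in Section 3.2, and its severe form (transplant or death) is listed there as an important potential risk. The combined transaminase and bilirubin criterion is the only one of the three that requires both abnormalities together. One would expect a stop at that threshold to hold for as long as the drug is given. Here the sentence that follows the mandatory list relaxes it after 24 weeks of exposure and leaves nothing out.

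What is at stake is participant safety and consistency between sites, not an endpoint or an estimate. Two sites could handle the same late event differently: one stops permanently because the list requires it, and the other holds the drug, consults and considers a restart because the clause allows it. The protocol does not say which instruction prevails.

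**Working it through.** The protocol states no figure for this point, so the check is mainly a comparison of texts.

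**1. Does the clause reach the combined criterion?** It covers elevated LFTs. Footnote g of Table 2 and the LFT row of Table 8 both count bilirubin as an LFT alongside AST and ALT. The clause comes directly after the three permanent stops and before the heading for the Liver Function Testing criteria, so those stops are its nearest antecedent. It names no exclusion. All 3 of the 3 immediate criteria fall under it.

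**2. Does the rechallenge bar survive?** It applies only where permanent discontinuation is required. If the decision may be taken case by case, the bar is not clearly triggered. For a confirmed elevation between 3× and 5× ULN, Section 6.4.4.1 sets a restart test: a fall below ULN or below baseline, with no hyperbilirubinemia. No such test is written for a combined elevation handled under the clause.

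**3. Does another section restore the stop?**
- Section 5.6.1 refers liver stops back to Section 6.4.4, so it inherits the clause.
- Sections 5.6.1 and 5.6.2 require withdrawal for events that endanger the participant's safety. The consequence is mandatory, but deciding that an event qualifies takes judgement.
- Section 5.6.2 makes an interruption of more than 30 days permanent. A restart within 30 days is not ruled out.
- The Hepatology Assessment Committee reviews suspected cases. Its assessment goes to the data monitoring committees for consideration.

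**4. Is an exposure limit usual in this section?** In the legible text, no permanent stop for neutrophils, platelets, amylase/lipase or creatinine has one. Nor does the general rule: "For any other laboratory abnormality of Grade 4 severity, the IMP should be permanently withdrawn". One block after the hepatic panel list is redacted, so this covers visible text only.

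**5. For how long does the clause apply?** Let E be the maximum planned weeks on evobrutinib. The share after 24 weeks of exposure is (E − 24)/E. The inputs are the 48-week main study, the placebo switch at Week 24 and the 384-week OLE (Sections 1 and 5.1). Gaps and interruptions are ignored.

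| Starting arm | E (weeks) | (E − 24)/E | Same, if the OLE ended at Week 240 |
|---|---|---|---|
| Evobrutinib | 48 + 384 = 432 | 408/432 = 94.4% | 264/288 = 91.7% |
| Placebo | 24 + 384 = 408 | 384/408 = 94.1% | 240/264 = 90.9% |
| Tecfidera | 384 | 360/384 = 93.8% | 216/240 = 90.0% |

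Week 240 is the label of the last interim analysis in SAP Section 8. It is used as a sensitivity value because the documents do not give actual exposure.

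**The case against.** The strongest reply is that this is a deliberate and supervised exception. The clause is permissive: the decision may be taken case by case, and an Investigator can still stop every such participant. Individual judgement with the Medical Monitor, backed by independent hepatologists, is a legitimate way to manage late elevations. Around it stand the general withhold-or-withdraw rule, the discussion before restarting, weekly monitoring for 12 weeks after any rechallenge, and the safety withdrawal rules. A participant whose bilirubin is still above 2× ULN would also fail the restart test written for milder elevations. Finally, SAP Section 5 records that the study terminated early, so few or no participants would benefit from an edit now.

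Most of this stands, and it limits the practical effect. It does not answer the narrow point. None of these rules says that a participant who meets the combined criterion after 24 weeks must stop permanently and may not restart. The milder-case restart test is not written for this case. If the sponsor meant the clause to reach only lesser elevations, the text does not say so.

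A reader might infer that the clause permits uninterrupted dosing through a combined elevation. The documents do not support that, because the section opens with withholding or withdrawal for the listed abnormalities. What becomes discretionary is the permanent stop.

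**Conclusion.** The point holds in a limited form. After 24 weeks of evobrutinib the combined stop, and the rechallenge bar tied to it, are not unconditionally mandatory on a literal reading. This rests on bilirubin counting as an LFT, on the clause applying to the stops just before it, and on the legible text alone.

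Three further inferences go beyond the documents.

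- *Every permanent liver stop becomes discretionary.* The recheck-based permanent stops come under the later Liver Function Testing heading, and the clause is not shown to reach them.
- *Table 7 contradicts the text.* It appears to list the same stops without the exception. However, the cell shading that would tie the permanent-withdrawal key to the liver cells is lost, so the mapping is inferred, and the table is titled as guidelines. This is at most weak support.
- *About 94% of liver risk falls under the clause.* The share counts planned calendar time, not liver events. Section 7.1.3 monitors chemistry every 2 weeks for the first 16 weeks of treatment or after a dose increase, and then every 4 weeks, so the plan itself does not treat all weeks alike. The visible documents also do not show when the clause was added, so the share should not be read as time actually spent under it.

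This is a cheap patient-safety improvement. It does not affect any analysis.

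**What to change.** In Section 6.4.4.1, state that ALT/AST > 3× ULN with total bilirubin > 2× ULN requires permanent discontinuation, with no rechallenge, at any duration of exposure. Limit the case-by-case clause to the other liver criteria, and require the drug to be held while the decision is made. Add a matching footnote to the liver rows of Table 7 so that table and text agree. No new threshold is needed.

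The cost is a short change to the text, one footnote, and slightly less discretion for the Investigator and Medical Monitor. Because the study ended early, the prospective benefit within this trial is small.
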